9.2.2.4 Statistical testing and multi-variable analysis

Given an appropriate reference population, the usual tests for statistical significance: chi-square or Fischer's exact test for the proportions or t-tests for continuous (interval-scale) variables (such as birth weight) will be used to evaluate the statistical significance of differences in event rates between pregnancies exposed to ella® versus those in the reference group (unexposed) pregnancies. Given a sufficiently large sample size for pregnancies exposed to ella®, multi-variable models (multiple linear and logistic regression for continuous and binary outcomes, respectively) will be used to assess the effects of risk factors for adverse outcomes in pregnancies exposed to ella®. This will be helpful in part for evaluating whether any particular adverse events in pregnancies exposed to ella® are due to known risk factors for these events or to suggest groups of women who may be at high risk for certain adverse events to determine whether precautionary measures (close surveillance / relative contraindications) may be indicated for certain groups of women.

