9 STATISTICAL PROCEDURES

9.1 Sample size justification

As described below, a sample size of 400 pregnancies with known outcomes was chosen as it provides 80% power to detect a two-fold increase (Risk Ratio=2) for events with a proportion of 3% and a three-fold increase (RR=3) for events with a proportion of 1% (e.g., approximately equivalent to the total prevalence of congenital heart defects) (refer to Annex 1).

Sample size and confidence interval calculations were done using Stata (version 11, Statacorp) and EpiInfo (CDC, Atlanta, GA) software programs.

Estimates for sample size requirements were performed with the goal of detecting a signal, if one exists, of an increase in the proportion of adverse pregnancy outcomes for pregnancies exposed to ella® compared to a given reference population. For these calculations, it is assumed that event rates / proportions would be comparable for an unexposed population and its corresponding source population, as by far most (essentially all) pregnancies in the source population would be unexposed to ella®.

Sample size calculations were performed assuming a type-I (alpha) error rate of 0.05, two-sided tests and a ratio of exposed to unexposed group of 1:10. Higher ratios (e.g., 1:6 or 1:4) would require somewhat higher sample sizes for the exposed group (detailed calculations are not shown) but the difference would be relatively small as the main determinant of study power will be the number of pregnancies exposed to ella®.

Pregnancies exposed to ella® will come from various population sources. In this context, stratified analyses for country-specific (or regional) outcomes may be helpful but would pose substantial limits as to the power for detecting the statistical significance of any observed differences.

Various sources of data may be found for large numbers of (essentially all) unexposed pregnancies for different adverse pregnancy outcomes (e.g. for congenital anomalies, population-based data from registries for congenital anomalies, notably members of the European Surveillance of Congenital Anomalies, EUROCAT).

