These proportions (cumulative incidence) of adverse events and their 95% confidence intervals will be calculated for the overall sample as well as by country, in order to assess potential differences due to variations in clinical practice regarding the management of pregnancies and pregnancy complications. Results will also be presented by age.

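### The comparison with the reference population is unadjusted, and the planned regression is confined to exposed pregnancies, so differences in age or country mix can create or hide a signal

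*Protocol*

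**What the plan says.** Protocol section 9.2.2.4, which applies once an appropriate reference population is available, names the tests: "chi-square or Fischer's exact test for the proportions or t-tests for continuous (interval-scale) variables (such as birth weight"). These "will be used to evaluate the statistical significance of differences in event rates between pregnancies exposed to ella" and those in the unexposed reference group. No stratification, standardisation or covariate adjustment is attached to them.

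The same section plans multiple linear and logistic regression, if the exposed sample is large enough. These models "will be used to assess the effects of risk factors for adverse outcomes in pregnancies exposed to ella". They are described as partly helpful for "evaluating whether any particular adverse events in pregnancies exposed to ella® are due to known risk factors", and for identifying groups of women at high risk.

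Age and country appear elsewhere as description of the exposed sample. Under section 9.2.2.2 the proportions "will be calculated for the overall sample as well as by country, in order to assess potential differences due to variations in clinical practice", and "Results will also be presented by age". Section 9.2.2.3 repeats this for the secondary outcomes. Section 9.1 says that country-specific stratified analyses might help but would have limited power, and does not commit to them.

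The exposed data are pooled. This study enrols women in the USA (section 4.3). Their data are combined with other trials and spontaneous reports (section 9.2.1) and with registry cases (section 9.2.2.2). For congenital anomalies, the example given for reference data is registries, "notably members of the European Surveillance of Congenital Anomalies, EUROCAT" (section 9.1).

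**The concern.** Section 9.2.2.2 gives the purpose of the primary objective as detecting a possible signal of concern. An unadjusted test against a general population reads that signal correctly only if exposed women would have had the reference risk without the drug. Users of emergency contraception need not have the age or country mix of all pregnancies, and a pooled sample need not match any one reference. The protocol itself expects results to vary by country.

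The assumption in section 9.1 does not cover this. It says that an unexposed population and its source population have similar rates because almost nobody is exposed. It does not say that exposed women resemble the reference in age or country.

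The regression does not close the gap. A model fitted to exposed pregnancies alone has no exposure contrast. It can rank risk factors among users, but it cannot change or explain the difference from the reference.

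Two errors are possible: a false alarm where the exposed carry more background risk, and a missed signal where they carry less.

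**Working it through.** **1. The protocol's own figure.** Inputs from section 9.1 and Annex 1 Table 1: two-sided alpha 0.05, power 80%, r = 10 reference pregnancies per exposed. With d = p1 − p0 and p̄ = (p1 + r·p0)/(r + 1):

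- n′ = [1.960·√((r+1)·p̄(1−p̄)) + 0.842·√(r·p1(1−p1) + p0(1−p0))]² / (r·d²)
- with continuity correction, n = (n′/4)·[1 + √(1 + 2(r+1)/(n′·r·d))]²

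For 3% v 6%, n′ = 362 and n = 398. For 1% v 3%, n′ = 339 and n = 392. These match Table 1, so the arithmetic is sound. It assumes that both groups share the same background risk.

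**2. Bias from one unbalanced risk factor.** The documents give no age- or country-specific rates, so these inputs are assumptions: a binary factor with risk ratio RRc of 1.5 or 2, prevalence 20% in the reference and pe in the exposed.

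Bias factor = [1 + pe(RRc − 1)] / [1 + 0.20(RRc − 1)]

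| pe | RRc = 1.5 | RRc = 2 |
|---|---|---|
| 5% | 1.025/1.10 = 0.932 | 1.05/1.20 = 0.875 |
| 10% | 1.05/1.10 = 0.955 | 1.10/1.20 = 0.917 |
| 30% | 1.15/1.10 = 1.045 | 1.30/1.20 = 1.083 |
| 40% | 1.20/1.10 = 1.091 | 1.40/1.20 = 1.167 |

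The crude risk ratio is therefore multiplied by 0.88 to 0.96 or by 1.05 to 1.17.

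**3. False positives under upward bias, no true effect.** Exact two-sided binomial test of 400 exposed against a fixed baseline, with true rate = baseline × bias:

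| Baseline | No bias | Bias 1.05 | Bias 1.167 |
|---|---|---|---|
| 20% | 4.6% | 7% | 35% |
| 3% | 3.9% | 4.3% | 7.8% |
| 1% | 3.9% | 4.2% | 5.7% |

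As a check, an uncorrected chi-square of 400 v 4,000 was enumerated exactly over both binomial counts. At the 20% baseline it rejects 8.1% and 36% of the time for the two biases. At 3% it rejects 5.8% and 10.2%, against 4.9% with no bias. The pattern is the same: material for common outcomes, modest for rare ones.

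**4. Power under downward bias, true RR = 2 at a 3% baseline.** Invert step 1 at n = 400 by n′ = (2n − c)²/(4n), with c = (r+1)/(r·d), and solve the n′ formula for power. The exposed rate is 6% × bias.

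| Bias | Exposed rate | Power |
|---|---|---|
| 1 | 6.00% | 80% |
| 0.955 | 5.73% | 74% |
| 0.9 | 5.40% | 65% |
| 0.875 | 5.25% | 60% |

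**5. Effect of standardising.** If the expected rate is computed on the exposed group's own mix of the factor, its bias factor is 1 by construction. The no-bias rows then apply for that factor.

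**The case against.** The strongest reply is that section 9.2.2 leaves the details to the statistical analysis plan, which is not shown and may add adjustment. Section 9.2.2.4 speaks of the usual tests and does not rule out a standardised comparison. That limits the point to what the protocol writes. It does not remove it, because the section names both the tests and the scope of the regression.

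Second, the comparison is conditional on an appropriate reference and is not the primary estimate, which is a proportion with an exact interval. No decision rule hangs on p < 0.05, and an independent board that includes a statistician trained in epidemiology reviews the cases (section 11). This stands: the test is one input to signal assessment. But no criterion for an appropriate reference is given, and a suitable registry can still differ in age mix.

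Third, stratification costs power (section 9.1). That is true of separate country tests. A standardised ratio keeps one overall comparison.

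A reader might also infer three stronger things that the documents do not support:

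- **That US women are to be compared with a European registry.** EUROCAT is only an example, for congenital anomalies. Section 9.1 expects various sources for different outcomes, and the pooled data are not from the USA alone.
- **That the protocol claims its regression will explain an excess over the reference.** It calls the models helpful in part for judging events among exposed pregnancies.
- **That nearly half of null comparisons would be falsely positive.** That rate (47% at a 20% baseline) needs a bias of 1.2, outside the range of the single-factor model above.

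**Conclusion.** The point holds as a cheap improvement. As written, the comparison with the reference is unadjusted, the regression cannot adjust it, and age and country are only described within the exposed sample.

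Neither the size nor the direction can be taken from the document. Under the assumed single risk factor, the false-positive rate for upward bias is about 7% to 35% at a 20% baseline, such as miscarriage. It stays near nominal, about 4% to 8%, at a 3% baseline. Downward bias matters more at the 3% design point that supports 400 pregnancies: power for a doubling falls from about 80% to about 60% to 75%. Larger or multiple imbalances would do more harm, and smaller ones less.

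**What to change.** Revise section 9.2.2.4 as follows:

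- **Binary outcomes.** Where the reference source gives rates by maternal age band, country or both, make the main comparison an observed/expected ratio. Take expected counts from those rates, applied to the age and country mix of the exposed cases.
- **Interval.** Use an exact Poisson interval for rare outcomes. For common outcomes use a binomial-based one, such as the exact interval for the observed proportion divided by the expected proportion. At 20% the Poisson variance is too large by 1/(1 − 0.20) = 1.25.
- **Incomplete reference data.** Standardise by whichever factor is available, and say which.
- **Birth weight.** Compare with age- or country-specific reference means where they exist, since an observed/expected count does not apply.
- **Crude tests.** Keep them as supportive.
- **Regression.** State that the exposed-only models do not adjust the comparison with the reference.

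The cost is a change of wording and reference tables by age and country, both of which the protocol already plans to report by. Some outcomes will lack stratified reference rates: Annex 1 Table 2 gives none. Other confounders, such as tobacco use, stay unadjusted.

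### A regression in ella-exposed pregnancies alone describes who is at higher risk; it cannot by itself support an ella-specific inference such as a relative contraindication

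*Protocol*

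**What the plan says.** Protocol 9.2.2.4 sets out two analyses.

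1. **Exposed against reference.** Chi-square, Fisher or t-tests assess "differences in event rates between pregnancies exposed to ella® versus those in the reference group (unexposed) pregnancies". No breakdown by risk factor is stated.
2. **Exposed only.** The text begins "Given a sufficiently large sample size for pregnancies exposed to ella®, multi-variable models" and says that these "will be used to assess the effects of risk factors for adverse outcomes in pregnancies exposed to ella". No unexposed pregnancies and no factor-by-exposure term are mentioned.

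The second analysis is described as partly helpful for two purposes: to judge whether events are "due to known risk factors for these events or to suggest groups of women who may be at high risk for certain adverse events". The second of these is carried further, to "suggest groups of women who may be at high risk for certain adverse events to determine whether precautionary measures" are called for, and the measures are then named: "precautionary measures (close surveillance / relative contraindications) may be indicated for certain groups of women".

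On size, section 9.1 states that "a sample size of 400 pregnancies with known outcomes was chosen", with a "type-I (alpha) error rate of 0.05, two-sided tests and a ratio of exposed to unexposed group of 1:10". That calculation concerns the first analysis, not the second.

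**The concern.** A relative contraindication is a statement about using the drug. It needs evidence that exposure changes risk in the group concerned. A coefficient for age or smoking, estimated among exposed women only, combines two things: the factor's ordinary effect in any pregnancy, and any extra effect of ella in women with that factor. The exposed data give only the combination.

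The error can run either way. An ordinary risk factor could be taken as a reason to restrict ella in a group. Equally, real harm concentrated in a group could be put down to a known risk factor, which is the model's other stated purpose. Adjusting the overall comparison with the reference perfectly would not help, because that comparison is not made within risk-factor groups.

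**Working it through.** **1. The protocol's own figure.** Annex 1, Table 1 gives 398 exposed pregnancies for 3% v 6% and 392 for 1% v 3%. With r = 10 unexposed per exposed, P = (p1 + r·p0)/(1 + r) and d = p1 − p0:

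n = [1.96·√((1 + 1/r)·P(1 − P)) + 0.842·√(p1(1 − p1) + p0(1 − p0)/r)]² / d²

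n_cc = (n/4)·[1 + √(1 + 2(r + 1)/(n·r·d))]²

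- 3% v 6%: P = 0.0327, n = 362, n_cc = 398.
- 1% v 3%: P = 0.0118, n = 339, n_cc = 392.

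Both stated figures reproduce with the continuity correction. They size the exposed-v-reference test and say nothing about subgroup inference.

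**2. What the exposed-only model can identify.** Let x = 1 in the risk group, b the log risk ratio of the factor without ella, e the log effect of ella when x = 0, and d the extra log effect of ella when x = 1. Among exposed women:

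log risk = (a + e) + (b + d)·x

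Only b + d can be estimated. Two opposite situations therefore give the same exposed data (340 v 60 pregnancies):

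| | Ordinary factor, ella harmless | No ordinary effect, ella doubles risk in the group |
|---|---|---|
| Unexposed risk, x=0 / x=1 | 17% / 34% | 17% / 17% |
| Exposed risk, x=0 / x=1 | 17% / 34% | 17% / 34% |
| Mean exposed events, x=0 / x=1 | 57.8 / 20.4 | 57.8 / 20.4 |
| Expected at same-group reference, x=1 | 60 × 0.34 = 20.4 | 60 × 0.17 = 10.2 |
| Observed/expected, x=1 | 1.0 | 2.0 |

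The regression sees only the second and third rows, which are identical. The last row separates the two cases, and it needs a reference rate for the same group.

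**3. How often an ordinary factor would reach p<0.05.** Assumptions not in the protocol: no drug effect, a binary factor, 60 of 400 exposed pregnancies in the group, 17% risk in the other 340, and a two-sided test at 0.05. With P = (60·p1 + 340·p0)/400, SE0 = √(P(1 − P)(1/60 + 1/340)) and SE1 = √(p1(1 − p1)/60 + p0(1 − p0)/340), the power is approximately Φ[(p1 − p0 − 1.96·SE0)/SE1].

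- RR 1.5: p1 = 0.255, P = 0.183, SE0 = 0.0541, SE1 = 0.0598. Φ(−0.35) = 36%.
- RR 2: p1 = 0.34, P = 0.196, SE0 = 0.0555, SE1 = 0.0645. Φ(0.95) = 83%.

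Simulation of the uncorrected chi-square (4,000 replicates) gives 36% and 83.5%, hence about 84%. With a continuity correction the figures are 30% and 79%. With RR 1 the rate is 5% or less.

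**4. Sensitivity to the outcome rate.** The same formula, with 400 exposed and an assumed 30% in the group (120 v 280). The overall rates are those used as baselines in section 9.1; p0 = overall rate/(0.7 + 0.3·RR):

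| Overall rate | RR 1.5 | RR 2 | RR 3 |
|---|---|---|---|
| 20% | 51% | 93% | >99% |
| 10% | 28% | 64% | 94% |
| 5% | 17% | 38% | 71% |
| 3% | 12% | 26% | 52% |

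Example at 3% and RR 2: p0 = 0.03/1.3 = 0.0231, p1 = 0.0462, SE0 = 0.0186, SE1 = 0.0212. Φ(−0.63) = 26%.

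**5. A within-group comparison.** A simulated factor-by-exposure interaction test, with 400 exposed and 4,000 unexposed pregnancies (the 1:10 ratio), is significant in about 2% to 5% of studies when ella is harmless. Suppose ella doubles risk in a group of 30% with ordinary RR 1.5. Its power is then about 99%, 74% and 25% at overall rates of 20%, 10% and 3%.

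**The case against.** The section is tentative. The models are run only if the sample allows, they are said to help in part, and they may suggest groups for which measures may be indicated. No threshold or decision rule turns a coefficient into a warning. The first stated purpose shows that the authors know an association may be ordinary. Further detail is deferred to the SAP (9.2.2), which is not at hand. Results are also shown by age (9.2.2.2), and the DMB weighs associated risk factors case by case (11.1).

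Much of this stands. A reader might infer that the plan would base contraindications on this regression, that a harmless drug would often be flagged, or that the type-I error of a subgroup warning equals the power to find an ordinary risk factor. The text supports none of these. The percentages above are the power to detect a true risk factor, and that detection is correct in itself. They become errors only if the association is then attributed to ella. They also come from a single-factor test with assumed group size and risk ratio, not from the planned multivariable model.

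Nor are all the named measures affected alike. Close surveillance can be argued from absolute risk whatever its cause; the difficulty lies in the relative contraindications.

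What the objection does not remove is the stated inference. The section assigns the exposed-only model a question that it cannot answer. The age breakdown consists of proportions among exposed pregnancies, the DMB judges single cases, and the reference test is overall. None of them is stated to compare a risk-factor group with unexposed women.

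**Conclusion.** The point holds as a fault in a stated inference. Section 9.2.2.4 names an exposed-only regression as helping to determine whether relative contraindications may be indicated. By construction, that model cannot separate ordinary risk from ella-specific harm, in either direction. This part needs no numerical assumption.

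The size does rest on assumptions. With no drug effect, a 340/60 split and 17% base risk, an ordinary factor reaches p<0.05 in about 36% (RR 1.5) or 84% (RR 2) of studies. For a 3% outcome, with 30% of women in the group, the range is about 12% to 26%. The scope for misreading is therefore large for common outcomes such as miscarriage and smaller for rare ones. The analysis is conditional and exploratory, and the primary estimation of outcome rates is unaffected.

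**What to change.** In section 9.2.2.4, and in the SAP to match:

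- Label the exposed-only model as descriptive of prognostic factors, that is, of absolute risk among exposed women. State that it does not by itself support any ella-specific inference, such as a relative contraindication, and does not by itself show that events are unrelated to ella.
- Base any group-specific inference about ella on observed versus expected events within the group. Take the expected count from a reference rate for the same group (for example age band), and test whether the observed/expected ratio differs between groups.
- Where no group-specific reference rate exists, draw no ella-specific subgroup conclusion.

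Descriptive use of the model for absolute risk can stay. This proposes no clinical rule.

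The cost is a wording change in both documents and a search for reference data broken down by the same factors. Annex 1, Table 2 gives only overall EUROCAT prevalences, so for many factors no conclusion will be available. Fewer subgroup statements will be possible, and for rare outcomes the power to see a difference between groups will be low (about 25% in the 3% example).

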10 SPONSOR PHARMACOVIGILANCE RESPONSIBILITIES

Whenever applicable, Individual Case Safety Reports will be reported to Health Authorities on an expedited basis according to current regulation (i.e. in no case later than 15 calendar days from receipt (see GVP Module VI EMA/873138/201 and 21 CFR for the USA).

This includes:

- Reports of congenital anomalies or development delay in the fetus or in the baby
- Reports of fetal death and spontaneous abortion.
- Reports of suspected adverse reactions (ADRs) in babies that are classified as serious.
- Reports of pregnancies resulting from ella® failure reported as required in GVP module VI for reports of lack of therapeutic efficacy for contraceptive.

Unintended pregnancy reports (i.e. reports of pregnancies inadvertently exposed to ella® without outcome data or with normal outcome) are considered as not serious by the company.

Reports of the aggregate data concerning pregnancies will be compiled and submitted to Health Authorities via Periodic Safety Update Reports (PSUR).

11 DATA MONITORING BOARD

An independent board of experts will evaluate outcomes of exposed pregnancies reported to the Sponsor's Pharmacovigilance department. All pregnancies entered in the pharmacovigilance database (all clinical studies, European registry, spontaneous pharmacovigilance reporting) will be reviewed and assessed by the board. It is a multidisciplinary and multinational board including the following medical specialties:

- 1 Obstetrics–Gynaecology/Reproductive Endocrinology specialist;
- 1 Dysmorphologist specialized in congenital anomalies;
- 1 Paediatrician specialized in neonatology;
- 1 Statistician with a sub-specialty in epidemiology.

This group will serve as an autonomous independent pregnancy Data Monitoring Board (DMB) reviewing all reported pregnancies from all sources (all past and current clinical trials including the ellipse II study, European registry and spontaneous pharmacovigilance case reports) periodically reviewing the reported outcomes of all pregnancies exposed to ella® by batches of 50. Moreover if specific safety issues are detected, a DMB meeting may be called by HRA Pharma.

